6.5.2 Blinding

As a pragmatic trial, this is non-blinded for the participants. Neither schools, nor teachers, nor students, nor clinicians will be blinded. Clinicians will work in teams that only provide either simple or complex prevention. The analysts will be blinded as to the care provided to students in a particular school.

6.6 Compliance Assessment

This intervention trial depends on protocol compliance by clinicians, not students. We will train and calibrate clinicians during the summer before beginning each school year. To assess compliance, we will use qualitative and quantitative methods together with audit and feedback. Qualitatively, to ensure that the electronic records reflect actual implementation, we will visit each team in the fall and spring of each year for a one-day site visit. During the day, we will monitor adherence to protocol, particularly: student flow, caries diagnosis, and procedures delivered.

Quantitatively, we will use the elementary methods of statistical process control^{27,28}. We will examine four domains: 1) informed consent rates; 2) caries prevalence (e.g.: diagnosis); 3) care provision; and 4) outcomes. We will monitor these domains using electronic records and then verify with in-person site visits. We will start with national averages and standard deviations for school-based informed consent rate (35%), untreated caries prevalence of (21.5%). All children (100%) with permanent bicuspids and molars should receive either silver diamine fluoride (simple prevention) or traditional sealants (complex prevention) and fluoride varnish. All children (100%) with caries on their posterior teeth should receive either silver diamine fluoride (simple prevention).

We will create histograms, Pareto charts, and control charts, at the school, grade, and clinician level to identify common cause and special cause variation. Control limits will be adjusted yearly based on prior year data. If a clinician, school or grade exhibits variation that is out of the control range we will use this audit to work with the clinical team and school to provide feedback. We will continue this process during the school year.

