7.4 Interim Analysis

There are no interim analyses in this study.

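### Follow-up outcomes are charted by clinician during the trial and fed back to unblinded single-arm teams that appear to score them; the plan does not rule out a resulting drift toward non-inferiority

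*Combined protocol and SAP*

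**What the plan says.** Section 6.6 (Compliance Assessment) names the audited domains: "We will examine four domains: 1) informed consent rates; 2) caries prevalence (e.g.: diagnosis); 3) care provision; and 4) outcomes". It then says "We will create histograms, Pareto charts, and control charts, at the school, grade, and clinician level". When a clinician, school or grade is out of range, "we will use this audit to work with the clinical team and school to provide feedback", and "We will continue this process during the school year". Starting references are given for consent (35%) and untreated caries prevalence (21.5%), each as one national figure with no split by arm. None is given for outcomes. Afterwards, "Control limits will be adjusted yearly based on prior year data".

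Section 6.5.2 says no clinician is blinded and adds: "Clinicians will work in teams that only provide either simple or complex prevention".

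Section 3.2 makes caries status a visual and tactile judgement by trained clinicians. Section 6.1.6 has examination and preventive care carried out on the same care day. No separate outcome examiner is named anywhere.

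Two other sections describe contact with the field. Under 8.3 the clinical research associate contacts the clinical team about out-of-range results; under 8.11 the associate contacts the performance site about metrics outside control limits. Section 7.2 models caries prevalence as an outcome, so the second audit domain, once past baseline, is also trial outcome data. Section 7.4 states: "There are no interim analyses in this study".

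**The concern.** Every clinician belongs to one arm, so a clinician-level outcome chart shows outcomes by arm to anyone who knows the team. If simple prevention truly arrests fewer lesions, its teams will tend to lie on one side of a shared centre line, and the chart may label that as special-cause variation. The people told so are unblinded and, apparently, score the next visit by judgement.

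Movement of recorded results toward a shared value makes the arms look more alike. In a superiority trial that costs power. In a non-inferiority trial it is the anti-conservative direction. Blinding the analysts (5.7, 6.5.2) does not help, because the change would already be in the data, and the analysis could not separate it from a true lack of difference.

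**Working it through.** **1. The plan's own figure.** Section 7.1 assumes 20% success in both arms, a margin of 10 points, alpha 5% and power 80%. n per group = 2 × 0.20 × 0.80 × (1.645 + 0.842)² / 0.10² = 198. This reproduces with a one-sided 5% alpha; one-sided 2.5% would give 252. Design effect = 1 + (235 − 1) × 0.10 = 24.4, and 396 × 24.4 = 9,662. The figure holds and says nothing about the audit. I reuse its one-sided 5%, ICC of 0.10 and cluster size.

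**2. What is stated and what is not.**
- Stated: outcomes and prevalence are charted by clinician during the trial; outliers are fed back; clinicians are unblinded and single-arm.
- Strong inference: treating teams score the outcome (3.2 with 6.1.6, and no other examiner named).
- Not stated: whether outcome limits are pooled or arm-specific, how limits are computed, and what feedback on an outcome may ask a team to change.

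**3. Are limits common to both arms?** The single 21.5% starting prevalence suggests so for that domain. Section 7.1 expects about 40% at baseline. If limits were binomial 3-sigma with 235 children per school (an assumption, since the standard deviation is not given), they would be 21.5% ± 3 × √(0.215 × 0.785 / 235) = 21.5% ± 8.0 points. A school at 40% would be out of range from the start.

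**4. Would a true arm difference be flagged?** Take complex 20% and simple 10%: each arm lies 5 points from the pooled 15%.
- Binomial 3-sigma limits, 3 × √(0.15 × 0.85 / n): ±3.4 points at 1,000 lesions and ±6.2 at 300 (assumed counts). At a 50% rate they would be ±4.7 and ±8.7.
- Limits that include between-school variation at ICC 0.10: the between-school SD is √(0.10 × 0.20 × 0.80) = 0.126, so ±38 points for one school. For a clinician averaging 3 or 6 schools (assumed) they are ±22 or ±15 points.

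A 5-point deviation can therefore be flagged or missed, depending on a formula that the plan does not give.

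**5. If the recorded difference shrinks by a share f.** Assume 30 schools per arm and 0.40 × 235 = 94 children with caries per school. SE at the margin = √{(0.20 × 0.80 + 0.10 × 0.90) × (0.10 + 0.90/94) / 30} = 0.0302. The chance of falsely declaring non-inferiority is Φ(f × 0.10 / SE − 1.645):

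| f | 94 per school | 235 per school (SE 0.0294) |
|---|---|---|
| 0 | 0.05 | 0.05 |
| 10% | 0.09 | 0.10 |
| 25% | 0.21 | 0.21 |
| 50% | 0.50 | 0.52 |

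**6. Pooled against arm-specific limits.** In a simulation with a true difference of −0.10, ICC 0.10, 94 children per school and binomial 3-sigma clinician charts, each flagged clinician's recorded rate moves a share g toward the centre line. There are 10 clinicians per arm with three schools each, or 30 with one each. The share g and the clinician numbers are assumptions.

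| Limits | g | Recorded difference | False non-inferiority |
|---|---|---|---|
| Pooled | 0.25 | about −0.08 | 0.15 to 0.22 |
| Pooled | 0.50 | about −0.06 | 0.46 to 0.74 |
| Arm-specific | 0.25 to 1 | −0.100 to −0.107 | 0.06 to 0.20 |

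With arm-specific limits the arms do not converge. The remaining inflation arises because pulling outliers in compresses the between-school variance. Pooled charts flagged 36% to 50% of clinicians, which reflects binomial limits applied to clustered data.

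**The case against.** The section's purpose is compliance. Feedback follows verification by site visits that observe diagnosis, clinicians are recalibrated each summer, and 3.2 ties the criteria to national survey and WHO standards. Nothing tells an examiner to move scores toward a target, and correcting real examiner drift would improve validity in an unblinded trial. Limits that allow for the plan's own ICC might never flag a 5-point shift, and yearly resetting could absorb a persistent arm difference. All of this stands, and it is why no size can be assigned.

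Three stronger readings are tempting and are not supported:
- A reader might infer that the audit does pull the arms together. That needs both shared limits and feedback that changes scoring, and the text states neither.
- A reader might infer that narrow limits such as ±4.7 points would flag any difference near the margin. Those limits rest on an assumed 50% rate and assumed lesion counts, and they ignore the ICC.
- A reader might infer a contradiction with 7.4. A quality chart has no between-arm test, no alpha spending and no efficacy decision rule, and 8.14 confines report tables to aggregate data. The charts do reveal outcomes by arm, which fits poorly with that masking, but they are not an interim analysis.

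What survives is that 6.6 states a rule rather than leaving a gap: outcomes are on the charts, and outliers go back to single-arm, unblinded teams. Calibration can control drift without using trial outcomes for feedback.

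**Conclusion.** The point holds as a permitted bias risk, not as a demonstrated bias. The plan sends follow-up outcome signals, and follow-up prevalence signals, to unblinded single-arm teams that appear to score those outcomes. It does not rule out common limits or an effect on scoring. If both occur, the direction favours non-inferiority.

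The size cannot be derived from the documents. The illustrations show only that modest shrinkage would matter: a quarter of a true 10-point deficit takes the error rate from 5% to about 21%. They rest on an assumed amount of shrinkage, 20% against 10% success, ICC 0.10 and 30 schools per arm. That treating teams score the outcome is inferred from 3.2 and 6.1.6. I would treat this as a worthwhile low-cost improvement, with medium confidence.

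**What to change.** - In 6.6, remove outcomes and post-baseline caries prevalence from the domains fed back to clinical teams. Keep feedback on consent, care provision and baseline diagnosis.
- Apply the same limit to the contact routes in 8.3 and 8.11; otherwise the information could reach the teams another way.
- Keep the annual calibration and the fall and spring site visits as the control on examiner drift.
- Let only the data coordinating centre review follow-up outcome data, for recording errors, with no outcome-level feedback to scoring teams until the primary endpoint data are complete (2 years for arrest and 3 years for prevention, under 3.2).

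Stating only that limits are arm-specific would be a weaker remedy. It removes the convergence but, in the illustration above, not the inflation from compressed between-school variance.

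The cost is a wording amendment and the loss of in-trial outcome feedback to teams. No change to sample size, visits or analysis is needed.

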6.7 Prior and Concomitant Therapy

NA

6.8 Receiving, Storage, Transporting, Dispensing, Breakdown and Disposal of Clinical Supplies

6.8.1 Receiving

The products used for this trial are typical standard of care (SOC) dental commodities obtained from Henry Schien and Elevate Oral Care. They include toothbrushes, toothpaste, bibs, gauze, q-tips, floss, fluoride varnish, silver diamine fluoride (a topical varnish used to treat and prevent dental caries and relieve dentinal hypersensitivity, and glass ionomer cement (a dental restorative material used in dentistry for dental fillings) and all personal protective equipment (PPE). They are shipped to NYUCD and stored in a locked closet until used on the 8th floor with other clinical supplies. The same products will be safely transported to the participant schools or the local community-based location for study use.

6.8.2 Storage

All supplies when not in use are stored in a locked closet on the 8th floor at NYUCD.

6.8.3 Transporting

Supplies are transported to and from the schools or community-based location in locked roller suitcases or locked backpacks. Non disposable contaminated instruments are placed in a lockable puncture resistant plastic container which is labeled with a biohazard sticker. The outside of the container is wiped down with an EPA registered intermediate level surface disinfectant. Disposable sharp

instruments are then placed in red biohazard bags, with a biohazard label affixed to the outside of the bag. The bag is then transported in a combination locked Agnus Bag (suitcase) to NYU for disposal per NYUCD protocol.

6.8.4 Dispensing

All supplies are removed from locked roller suitcases or locked backpacks. Using clean gloves clinical supplies are placed on a clean barrier protected table at least 6' apart from the treatment station and barrier protected dirty table.

6.8.5 Breakdown

After completing treatment, all non-used clinical supplies from the clean table are placed back in the suitcase or backpack. The outside of the suitcase and backpack are disinfected with an EPA registered intermediate level surface disinfectant and then locked and transported back to NYUCD where they are placed in a locked closet on the 8th floor.

6.8.6 Disposal

After each individual procedure is performed disposable items are brought to the barrier protected dirty table which is at least 6' away from the barrier protected clean table. Disposable items are placed in the trash. All non-disposable sharps are placed in the sharps container labeled with a biohazard sticker which is located under the barrier protected dirty tale. Solid waste is disposed of into the receptacles lined with clear plastic bags. If any of the materials contain or may contain absorbed droplets of blood, they are placed in a red biohazard bag with a biohazard label affixed to the outside of the bag. The bag is then transported in a combination locked Agnus Bag (suitcase) to NYU for disposal per NYUCD protocol.

Study Procedures

6.9 Study Procedures Table

Following stratification and solicitation, execution of MOU with individual schools, communitybased organizations, and randomization, care will be provided in a school, at a communitybased location, or at NYUCD. In year 1 care will be offered in 30 schools, and in year 2 an additional 46 schools. In year 3 care will also be offered at a community-based location and at NYUCD.

7 Statistical Plan

7.1 Sample Size Determination

The study is powered to the primary outcomes of caries arrest and caries prevention between twice-yearly simple and complex prevention. We expect to enroll approximately 14,100 students across the initial 60 schools over the duration of the study (N=235 per cluster). The remaining 16 schools will contribute approximately 3760 participants. From our pilot studies of school-based caries prevention, baseline caries prevalence is approximately 40%. Our power estimates assume an equal proportion of success, π , of 20% caries arrest. With a given non-inferiority margin (δ) of 10%, a total sample size per group of 198 (N_{tot} = 396) is required for an alpha of 5% and a power of 80%²⁹. However, as we use a cluster randomized design, this sample size is inflated to account for clustering (intraclass correlation coefficient = .10) by a design effect of 24.4 to a total required sample of 9,662.

For caries prevention, both interim therapeutic restorations and silver diamine fluoride have been shown to be 80% efficacious in individual clinical trials. Power for the repeated measures design was estimated using the method of Diggle et al (2002) for generalized estimating equations ³⁰. For power estimates, we control for the baseline prevalence of untreated decay. We assume a conservative average number of visits per child of 6, with a power of .80 and an alpha of 5%. We further assume a repeated measures correlation of 0.5 and a per-visit attrition rate of 20%. For a given minimally detectable effect size (standardized effect size difference) of .25, an attrition and clustering adjusted sample size of 12,874 is required. Thus, our study is powered for these conservative assumptions for caries prevention. Further, we note that in the presence of the nonlinear link function, ME-GLM is more powerful than GEE, thus our power estimates are conservative and the anticipated sample size is sufficient for analysis.

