1.2 Study Aims

The overall goal of this study is to measurably improve oral health equity. Towards this goal, we will compare "simple" and "complex" prevention, two packages of interventions designed to prevent and arrest dental caries. The study design is a cluster randomized non-inferiority pragmatic trial. Both preventive interventions are expected to be equally effective in improving health equity. The major difference in the two protocols is that "simple" prevention costs

approximately 25% of "complex" prevention. Simple also takes approximately 25% of the time of complex prevention. Therefore, if simple and complex are found to be equally effective, for the same time and cost, simple prevention could improve health and health equity to approximately 3 times the number of children as complex prevention.

Our prior work, and data from systematic reviews, indicates that the protocols we propose should be similarly effective in both arresting current caries and preventing subsequent caries by 50% to 80%. Thus all children should benefit from the proposed preventions. We will collect data on oral health and child quality of life, and assess student academic performance.

The study consists of three groups: (1) a group receiving simple prevention twice per year; (2) a group receiving complex prevention twice per year; and (3) a group receiving simple prevention once per year.

We will select 76 elementary schools to participate in the program over a five-year period. 30 elementary schools will be randomized to receive simple prevention twice per year and 30 elementary schools will be randomized to receive complex prevention twice per year. The remaining 16 schools will receive simple prevention once per year. The care will be provided in schools, community-based locations or at the New York University College of Dentistry.

The inclusion criteria for the schools enrolled in groups (1) and (2) include: A Hispanic/Latino population of at least 50% and a free and reduced lunch population of at least 80%. The remaining racial/ethnic and socioeconomic distribution of these schools will include children from any race/ethnicity and economic background. The inclusion criteria for schools in group (3) include any elementary school in New York City and will be selected to include representation from every major racial/ethnic group and socioeconomic level.

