1.4.3 Potential Benefits

There are three distinct benefits.

1. The benefit to all participants is that they will receive either primary or primary and secondary caries prevention once or twice yearly. The expectation is that both the simple and complex will reduce caries by 50% to 80%.

- 2. If, as we propose, simple prevention is as effective as complex, and simple prevention takes approximately 1/4 the time and 1/4 the cost of complex prevention, its use will increase access to effective care.
- 3. The methods to be applied and the outcomes identified both address national Healthy People 2020 goals.

Ultimately, evidence-based changes in knowledge, attitudes and practice among all patient and stakeholder partners will help reduce the continually high burden of caries in children, particularly among minority and low-SES children. Improved outcomes data should increase support for the sustainability of ongoing and new caries prevention programs at both a local and national level. The benefits to society include improved oral health for our children that is sustained by a system of preventive care that is more clinically and cost effective than the current method of care.

Numerous efficacy trials demonstrate the benefits of complex preventive dental care, which has far-reaching effects on physical and emotional health, nutrition, social interactions and employability. However, numerous barriers still exist to improvements in child oral health: an already-existing global and national burden of caries; the burden of disease in NYC; the social burden of disease, particularly affecting academic performance and psycho-social development; barriers to office-based care⁹; economic incentives to support treatment rather than prevention; the reduced efficacy of treatment to prevention; and large variation in care without outcome measures of effectiveness.

Without data to support the effectiveness of preventive oral health care, we predict that two things will occur (depending on state and local values and circumstances): 1) the current helter-skelter implementation of well-meaning but ineffective programs will continue; and/or 2) there will be an extinction of those public caries prevention programs that are truly effective.

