5.5 Prior and Concomitant Therapy

Prior therapy is noted on the clinical examination. The only concomitant therapy provided in this study is fluoride varnish. All children are referred to a local dentist or community health center for follow on care. However, our experience is that only approximately 10% of parents follow through. Therefore, we see children once or twice per year. Using complex prevention, we achieve ~50% reduction in untreated caries, and almost complete elimination of toothaches.

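### Section 7.1 labels 20% as the arrest success rate, at odds with the plan's own 50% to 80%; either the label or the assumed rate needs correcting

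*Combined protocol and SAP*

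**What the plan says.** **Section 7.1** sets an equal proportion of success in the two arms "of 20% caries arrest. With a given non-inferiority margin" of 10%. It states that "a total sample size per group of 198" "is required for an alpha of 5% and a power of 80" per cent. This is inflated for clustering ("N=235 per cluster", intraclass correlation 0.10) by a design effect of 24.4 to 9,662. Planned enrolment in the 60 randomized schools is about 14,100. No source is given for the 20%.

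**Section 1.2** expects the two protocols to be "similarly effective in both arresting current caries and preventing subsequent caries by 50% to 80" per cent.

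**Table 1 (Section 3.1)** lists 80% for arresting current caries, both for interim therapeutic restorations and for silver diamine fluoride.

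**Section 7.2** models the child-level percentage of arrested lesions. It writes the null as π(simple) − π(complex) ≥ δ and the alternative as π(simple) − π(complex) < δ, with δ = 10%.

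Two further statements concern disease reduction rather than arrest. Section 1.4.3 says "The expectation is that both the simple and complex will reduce caries by 50% to 80" per cent, and Section 5.5 says "Using complex prevention, we achieve ~50% reduction in untreated caries, and almost complete elimination of toothaches".

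**The concern.** Read literally, 7.1 assumes that one lesion in five is arrested under either regimen, while 1.2 and Table 1 expect between one half and four fifths. The rate matters in two ways.

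First, the sample size is proportional to π(1 − π). That product is 0.16 at 20%, the same 0.16 at 80%, and 0.25 at 50%. A value of 20% is therefore as favourable as the top of the plan's range and more favourable than the rest of it.

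Second, the meaning of a 10-point margin depends on the reference rate. From 80% arrest it tolerates 70%, a loss of one eighth. From 20% arrest it would tolerate 10%, a loss of half.

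Section 7.2 adds to the doubt. Its null, a difference of δ or more in the simple arm, describes inferiority only if a high π is bad. Section 7.1 calls π success. The two sections do not describe the same quantity in the same direction.

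**Working it through.** **Inputs from 7.1.** Margin 0.10; alpha 5%; power 80%; 235 children per school; intraclass correlation 0.10; 14,100 children in two equal arms (7,050 each). The sidedness of alpha is not stated.

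**Reproducing the plan's figure.** With equal true rates,

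n per group = (z₁₋α + z₀.₈)² × 2π(1 − π) / 0.10².

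At one-sided 5%, (1.645 + 0.8416)² ≈ 6.183. At π = 0.20, n = 618.3 × 0.32 = 197.8, rounded up to 198, as stated. One-sided 2.5% gives 252, so one-sided 5% is inferred. The design effect is 1 + (235 − 1) × 0.10 = 24.4, and 396 × 24.4 = 9,662.4. The plan's arithmetic is correct for its inputs.

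**Changing only the arrest rate.** Power at 14,100 is Φ(0.10 / √[2π(1 − π) × 24.4 / 7,050] − 1.645).

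| Arrest rate | 2π(1 − π) | n per group | Total × 24.4 | Change from 9,662 | Power at 14,100 |
|---|---|---|---|---|---|
| 80% (or 20%) | 0.32 | 198 | 9,662 | none | 91% |
| 70% | 0.42 | 260 | 12,688 | +31% | 84% |
| 60% | 0.48 | 297 | 14,494 | +50% | 79% |
| 50% | 0.50 | 310 | 15,128 | +57% | 78% |

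**Where 14,100 stops being enough.** The effective size per arm is 7,050 / 24.4 = 288.9. Setting 618.3 × 2π(1 − π) = 288.9 gives π(1 − π) = 0.2337, so π = 0.5 ± 0.128, or about 37% to 63%.

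**If only children with baseline caries contribute.** Section 7.1 puts baseline prevalence at about 40%: 0.40 × 235 = 94 per school, design effect 1 + 93 × 0.10 = 10.3, and 94 × 60 = 5,640 children (2,820 per arm). The requirement is 4,079 at 80% arrest (396 × 10.3) and 6,386 at 50% (620 × 10.3). Power with 5,640 is about 90% and 76% respectively.

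**The failure reading.** If π is failure, 20% is the complement of Table 1's 80% arrest. The direction of the 7.2 hypotheses then fits non-inferiority, and 9,662 is unchanged. Because π(1 − π) is symmetric, the table applies equally to failure rates of 20% to 50%, which correspond to the 50% to 80% arrest in 1.2.

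**The case against.** The strongest reply is that nothing is miscalculated. Table 1 holds the only figure given for arrest alone, 80%, and at 80% the requirement is exactly 9,662. With 7.2 written as if π were unfavourable, a mislabelled failure rate is a natural explanation and leaves the sample size intact. This stands as a plausible reading but is not proven: 7.1 says success, 7.2 has just described the percentage arrested, and 7.2 states its null in words as non-inferiority, so its own drafting is loose.

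Other parts of the reply also stand:

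- The analysed endpoint, lesions staying arrested for the whole study, is stricter than the efficacy quoted in 1.2 and Table 1, so the true rate could lie below 50%. The plan does not use this to justify 20%.
- Sections 1.4.3 and 5.5 speak of caries reduction, as does the footnote to Table 1. A reader might infer that every other figure in the plan contradicts 20%. Only 1.2 and Table 1 refer to arrest, and 1.2 gives one range for arrest and prevention together.
- A per-child proportion of lesions has variance no greater than π(1 − π), so 15,128 is an upper bound on the all-children basis. At 50% arrest, a variance about 7% lower (0.2337 / 0.25 = 0.935) would remove the shortfall against 14,100.

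The reply does not rescue 7.1 as written. On the failure reading the label is wrong; on the arrest reading the rate conflicts with 1.2 and Table 1.

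**Conclusion.** Section 7.1 needs correcting on either reading, in its label or in its assumed rate. On the failure reading the sample size is unaffected. On the arrest reading the requirement over the plan's 50% to 80% range runs from 15,128 down to 9,662, and power at 14,100 from about 78% up to 91%.

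A reader might infer that the trial is materially underpowered, or that 9,662 is 57% too low. The documents do not support this. At 50% arrest, 15,128 is 57% more than 9,662, which is the same as saying that 9,662 is 36% below 15,128. At 80% arrest there is no difference. The plan is to enrol 14,100, not 9,662, and at that size power dips only one to two points below target, and only for arrest of about 37% to 63%. A reader might also infer that the margin lets simple prevention arrest half as many lesions; that follows only if 20% truly is the arrest rate.

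These figures assume one-sided 5% (inferred), intraclass correlation 0.10, 235 children per school, no attrition, a binary outcome per child and all enrolled children contributing. At one-sided 2.5% the requirements would be larger (12,298 at 80% arrest, 19,178 at 50%). On the caries-only basis, power at 50% arrest is about 76%.

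**What to change.** 1. State in 7.1 and 7.2 whether π is arrest or failure, and write the hypotheses in the matching direction.
2. If 20% is failure, say so in 7.1, tie it to Table 1's 80% arrest, and state that the 10-point margin compares 80% with 70% arrest. If 20% is arrest, reconcile it with 1.2 and Table 1 or justify it.
3. Replace the single 9,662 with the requirement and power at 14,100 over 50% to 80% arrest, as tabulated above, and state the sidedness of alpha.
4. Note beside those figures that they treat the endpoint as binary per child, an upper bound on the variance, and count every enrolled child. Add the caries-only calculation for comparison.

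The cost is a text amendment and a less favourable power statement at the lower end of the range. Neither the number of schools nor the enrolment target has to change.
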